### 9.2. Prior and Concomitant Medications

Prior and concomitant medications will be captured in the electronic Case Report Form (eCRF) from 2 weeks prior to administration of gene replacement therapy through the last study visit.

#### 9.2.1. Prophylactic Administration of Prednisolone

An antigen specific T-cell response to the AAV vector was observed in the ongoing Phase 1 clinical study (AVXS-101-CL-101) investigating AVXS-101 treatment via IV infusion. This is an expected response between 2 to 4 weeks following gene replacement therapy. One possible consequence to such antigen specific T-cell response is clearance of the transduced cells and loss of transgene expression.

In an attempt to dampen the host immune response to the AAV based- therapy, all patients will receive prophylactic prednisolone at approximately 1 mg/kg/day beginning 24 hours prior to gene replacement therapy until at least 30 days post-infusion. After 30 days of treatment, the dose of prednisolone can be tapered for patients whose ALT values, AST values, and T-cell

response are  $\leq 2 \times$  ULN for ALT and AST, and  $< 100$  SFC/ $10^6$  PBMCs in accordance with the following treatment guideline:

- Until at least 30 days post-infusion: 1 mg/kg/day
- Weeks 5 and 6: 0.5 mg/kg/day
- Weeks 7 and 8: 0.25 mg/kg/day
- Week 9: prednisolone discontinued

If the AST or ALT values are  $> 2 \times$  ULN, or if T-cell response is  $\geq 100$  SFC/ $10^6$  PBMCs after 30 days of treatment, the dose of prednisolone will be maintained until the AST and ALT values decrease below threshold. If T-cell- response continues past Day 60, Investigator discretion should be used considering risk benefit for maintaining prednisolone. Variance from these recommendations will be at the discretion of the Investigator based on potential safety issues for each patient.

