In an attempt to dampen the host immune response to the adeno-associated virus (AAV) derived therapy, all patients will receive prophylactic prednisolone at approximately 1 mg/kg/day beginning 24 hours prior to AVXS-101 infusion until at least 30 days post-infusion. After 30 days of treatment, the dose of prednisolone can be tapered for patients whose alanine aminotransferase (ALT) values, aspartate aminotransferase (AST) values, and T-cell response are below the threshold of 2 X ULN for ALT and AST, and < 100 SFC/10^6 PBMCs in accordance with the following treatment guideline: 1 mg/kg/day until at least 30 days post-infusion, 0.5 mg/kg/day at Weeks 5 and 6, 0.25 mg/kg/day at Weeks 7 and 8, and discontinued at Week 9.

Efficacy will be assessed by achievement of the key developmental milestone of functional independent sitting for at least 30 seconds at the 18 months of age study visit and survival at 14 months of age. The ability to thrive (as defined above) and the ability to remain independent of ventilatory support (as defined above) will also be assessed at 18 months of age. Additional developmental milestones will be assessed using Bayley Scales of Infant and Toddler Development (Version 3). Safety will be assessed through monitoring adverse events (AEs), concomitant medication usage, physical examinations, vital sign assessments, cardiac assessments, and laboratory evaluations. A Data Safety Monitoring Board (DSMB) will review safety data on a quarterly basis and will also convene within 48 hours should any patient experience an unanticipated CTCAE Grade 3, or higher AE/toxicity that is possibly, probably, or

definitely related to gene replacement therapy, and is associated with clinical symptoms and/or requires medical treatment. This includes any patient death, important clinical laboratory finding, or any complication attributed to administration of gene replacement therapy. In such instances, the DSMB will review the safety information and provide its recommendation. The DSMB can recommend early termination of the study for safety reasons.

**Number of Patients (planned):** Up to twenty (20) patients that meet the study enrollment criteria to enable at least 15 patients that meet ITT criteria. Study enrollment will stop as soon as practical following enrollment of the fifteenth patient that meets the ITT criteria.

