**Table 3: Abbreviations and Specialist Terms**

Abbreviation or Specialist Term	Explanation
AAV	Adeno-associated virus
AAV9	Adeno-associated virus serotype 9
AE	Adverse event
ALT	Alanine aminotransferase
ASO	Antisense oligonucleotide
AST	Aspartate aminotransferase
BUN	Blood urea nitrogen
CB	Chicken- $\beta$ -actin-hybrid
CDC	Center for Disease Control
CFR	Code of Federal Regulations
cGMP	Current Good Manufacturing Practice
CI	CHOP-INTEND
CHOP-INTEND	Children's Hospital of Philadelphia Infant Test of Neuromuscular Disorders
CK	Creatine kinase
CK-MB	Creatine kinase isoenzyme
CLIA	Clinical Laboratory Improvement Amendment
CMAP	Compound motor action potential
CMV	Cytomegalovirus
CNS	Central nervous system
CTCAE	Common Terminology Criteria for Adverse Events
Day 1	First 24-hour interval after the start of gene replacement therapy infusion
Day -1	24-hour interval prior to the start of gene replacement therapy infusion
DSMB	Data Safety Monitoring Board
ECG	Electrocardiogram
eCRF	Electronic Case Report Form
ELISA	Enzyme-linked Immunosorbent Assay
ELISpot	Enzyme-linked ImmunoSpot
ET	Early termination
FVB	Friend Virus B-Type
GCP	Good Clinical Practice
GFP	Green fluorescent protein
GGT	Gamma glutamyl transferase
GLP	Good Laboratory Practice
HEENT	Head, eyes, ears, nose, and throat
HgB	Hemoglobin
HIV	Human Immunodeficiency Virus

Abbreviation or Specialist Term	Explanation
ICD-10 code	International Statistical Classification of Diseases and Related Health Problems
ICH	International Council for Harmonisation
IEC	Independent Ethics Committee
IFN- $\gamma$	Interferon gamma
INR	International normalized ratio
IRB	Institutional Review Board
ISF	Investigator site file
ITR	Inverted terminal repeat
ITT	Intent-to-treat
IV	Intravenous
LFE	Liver function enzymes
LFT	Liver function test
MedDRA	Medical Dictionary for Regulatory Activities
NHP	Non-human primates
NOAEL	No Observable Adverse Effect Level
OAE	Other significant Adverse Event
PBMC	Peripheral blood mononuclear cells
PICU	Pediatric intensive care unit
PNCR	Pediatric Neuromuscular Clinical Research Network
RNA	Ribonucleic acid
RSV	Respiratory syncytial virus
SAE	Serious adverse event
SAP	Statistical Analysis Plan
sc	Self-complementary
scAAV	Self-complimentary adeno-associated virus
scAAV9.CB.SMN	Self-complimentary adeno-associated virus serotype 9 chicken- $\beta$ -actin-hybrid survival motor neuron
SMA	Spinal muscular atrophy
SMN	Survival motor neuron
SMN1	Survival motor neuron 1 gene

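### Section 9.2.1 makes the start of the prednisolone taper depend on AST/ALT, but does not make the Week 9 stop depend on the AST/ALT already scheduled for Day 60/Month 2

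*Protocol*

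**What the plan says.** Section 9.2.1 sets one laboratory condition: "After 30 days of treatment, the dose of prednisolone can be tapered for patients whose ALT values, AST values, and T-cell" response are within limits, namely at or below 2 × ULN for both enzymes and under 100 SFC per 10^6 PBMCs. If a limit is exceeded after 30 days of treatment, the dose is held until AST and ALT come down.

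The steps are then listed by week: 0.5 mg/kg/day in Weeks 5 and 6, then "Weeks 7 and 8: 0.25 mg/kg/day", then "Week 9: prednisolone discontinued". The last two carry no laboratory condition. The Synopsis (Methodology) gives the same schedule: "0.25 mg/kg/day at Weeks 7 and 8, and discontinued at Week 9".

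Section 9.2.1 also contains softening text:
- The schedule is called a guideline, and "Variance from these recommendations will be at the discretion of the Investigator based on potential safety issues for each patient".
- If T-cell response continues past Day 60, "Investigator discretion should be used considering risk benefit for maintaining prednisolone". AST and ALT are not named there.
- On the timing of the T-cell response: "This is an expected response between 2 to 4 weeks following gene replacement therapy".

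On sampling, Section 12.1.10.2 ties chemistry to scheduled visits. Sections 11 and 12.1, Table 6 and Appendix 5 show no visit between Day 30 (±2) and Day 60/Month 2 (±7). Section 12.1.10 lets the investigator repeat clinically significant values and use a local laboratory.

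**The concern.** Section 5.4 reports that every treatment-related event in Phase 1 was a liver enzyme elevation without clinical symptoms, and that these resolved on prednisolone. Elevated liver enzymes are the named adverse event of special interest (Section 13.1.1.3) and a safety endpoint (Section 14.1.1.4).

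Consider a patient who passes the Day 30 check and then has a silent rise as the steroid is reduced. There is no symptom and no known abnormal value to prompt a discretionary test. The hold rule cannot act before the next scheduled sample, because there is no scheduled value to trigger it. The next sample is due at about the time of the stop, yet the text does not ask the site to read it first. At stake is the withdrawal of the drug that resolved these events in Phase 1, on a value about four weeks old, when a newer one is already planned.

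**Working it through.** This is calendar arithmetic. Inputs: Table 3 defines Day 1 as "First 24-hour interval after the start of gene replacement therapy infusion"; doses and weeks are from Section 9.2.1; windows are from Sections 11 and 12.1.

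**Is there an unlisted draw?** Table 6 rows at their maxima: 16.9 + 3.3 + 3.3 + 9.6 + 3.3 + 3.3 + 9.6 + 3.6 + 25.3 + 14.4 + 3.6 = 96.2 mL, which is the stated total. No extra draw lies between Day 30 and Day 60.

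**Stop day.** If 1 mg/kg/day runs through Day 30, the earliest reduced dose is on Day 31. Section 9.2.1 does not say how weeks are counted, so two calendars are used.
- A, weeks from infusion (Week w starts on Day 7(w−1)+1): 0.5 mg/kg on Days 31–42, 0.25 mg/kg on Days 43–56, first dose-free day 57. The taper lasts 26 days.
- B, two full weeks per step: 0.5 mg/kg on Days 31–44, 0.25 mg/kg on Days 45–58, first dose-free day 59. The taper lasts 28 days.

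**Age of the Day 30 AST/ALT (nominal dates, Day 31 start)**

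| | Calendar A | Calendar B | Range with Day 28–32 window |
|---|---|---|---|
| At the 0.25 mg/kg step | 43 − 30 = 13 days | 45 − 30 = 15 days | 43 − 32 = 11 to 45 − 28 = 17 |
| At the stop | 57 − 30 = 27 days | 59 − 30 = 29 days | 57 − 32 = 25 to 59 − 28 = 31 |

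**Gap without a scheduled draw.** Days 33–52 are 20 days: 20/26 = 77% of the taper under A, 20/28 = 71% under B.

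**Order of the stop and the Day 60 sample.** Nominally the sample follows the stop by 60 − 57 = 3 days (A) or 60 − 59 = 1 day (B). This order is not fixed:
- Other counting gives 0 days (30 days post-infusion taken as Day 31, plus 28 days) or 4 days (weeks counted from Day 0).
- The Day 60 window is Days 53–67, 15 days. Of these, 11 (Days 57–67, A) or 9 (Days 59–67, B) fall on or after the stop; the rest fall before it.
- Under B with start day s, the stop is s + 28. A start on Day 32 gives Day 60, and Day 33 gives Day 61. The start needs Day 30 results, and their turnaround is not stated. An assumed wait of 3 to 7 days gives starts on Days 33–37 and stops on Days 61–65, after nominal Day 60.
- Week 9 is Days 57–63 when counted from infusion, so it contains Day 60.

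Under every variant, the text does not make the stop depend on the Day 60 AST/ALT.

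**The case against.** The strongest points on the other side are these.

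- **The hold rule may be continuing.** Its reference to the time after 30 days has no end date, so it could cover any later raised value. This is a possible reading. It does not help before the next sample, because no scheduled AST/ALT between Day 30 and Day 60 can trigger it, and it does not tell a site to obtain the Day 60 value before stopping.
- **The order is not settled.** A reader might infer that prednisolone is always stopped 1 to 3 days before the Day 60 test. The documents do not support that. The interval needs a Day 31 start with no wait for Day 30 results, and Week 9 itself contains Day 60, so a site may wait. What stands is only that waiting is not required.
- **Sampling matches the expected risk.** Chemistry is drawn on Days 7, 14, 21 and 30, which covers the expected 2-to-4-week T-cell response. That supports the early schedule but does not address withdrawal of the steroid.
- **Discretion exists.** Investigators may vary the taper, repeat tests, use local laboratories and give corticosteroids later as routine care (Section 9.2.2). This limits the consequence. However, a silent rise after a normal Day 30 value gives no prompt to use that discretion.
- **Waiting prolongs steroid in infants with no known abnormality.** True; the amount is small on nominal dates and needs a cap.

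**Conclusion.** The point holds as a low-cost safety improvement. The start of the taper is properly conditional; the Week 9 stop is not, although the relevant test is already scheduled around it. A patient below threshold at Day 30 can be stopped on a value 27 to 29 days old on nominal dates (25 to 31 with the Day 30 window), assuming a Day 31 start and one of the two week-counting conventions.

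A reader might infer that the protocol exposes patients to a demonstrated liver risk. The documents do not show that: they give no frequency for enzyme rises during the taper, a persisting rise would be seen at Day 60, and steroid can be given again. Nor is there a finding about patients held on 1 mg/kg/day, since holding until the values fall already implies retesting. The case rests on the small cost of reading a planned test before the drug is withdrawn.

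**What to change.** In Section 9.2.1, extend the last step so that it reads: "Week 9: prednisolone discontinued" *once the Day 60/Month 2 AST and ALT are known and at or below 2 × ULN; until then continue 0.25 mg/kg/day. If either is above 2 × ULN, the existing hold rule in this section applies, subject to Investigator variance. If no value is available by Day 74, the Investigator decides.* Make the matching change in the Synopsis. Pointing a raised value to the existing hold rule avoids creating a second, softer rule.

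Day 74 is the window end plus the 7-day rescheduling allowance in Section 7.1 (67 + 7).

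The cost is two text changes, with no added visit or routine draw, so Table 6 stays at 96.2 mL. Repeat testing arises only if the Day 60 value is raised. The downside is more steroid. Planned exposure, with 31 days at full dose (Day −1 to Day 30), is:
- A: 31 × 1 + 12 × 0.5 + 14 × 0.25 = 40.5 mg/kg
- B: 31 × 1 + 14 × 0.5 + 14 × 0.25 = 41.5 mg/kg

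| Wait until | Calendar A | Calendar B |
|---|---|---|
| Day 60 | 3 days, 0.75 mg/kg (1.9%) | 1 day, 0.25 mg/kg (0.6%) |
| Day 67 | 10 days, 2.5 mg/kg (6.2%) | 8 days, 2.0 mg/kg (4.8%) |
| Day 74 cap | 17 days, 4.25 mg/kg (10.5%) | 15 days, 3.75 mg/kg (9.0%) |

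Each day of result turnaround adds 0.25 mg/kg (about 0.6%). Turnaround is not stated in the protocol; an assumed 1 to 7 days adds 0.25 to 1.75 mg/kg, within the cap. A result available before the stop adds nothing.

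The change leaves the 0.25 mg/kg step without a current value. One local AST/ALT at about Day 42–44 would cover that step, but it is an extra blood draw and is offered only as an option.

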### **9.2.2. Prohibited Medications**

Concomitant use of any of the following medications is prohibited:

- Drugs for treatment of diabetes, myopathy or neuropathy
- Therapy received with the intent to treat SMA (e.g., nusinersen, valproic acid)
  - Oral  $\beta$ -agonists must be discontinued at least 30 days prior to gene therapy dosing.
  - Inhaled  $\beta$ -agonists may be used to treat respiratory complications of SMA provided such medications are dosed at clinically appropriate levels
- Any investigational medication other than AVXS-101 is prohibited during the study
- Ongoing immunosuppressive therapy, plasmapheresis, immunomodulators such as adalimumab, or immunosuppressive therapy within 3 months of starting the study (e.g., corticosteroids, cyclosporine, tacrolimus, methotrexate, cyclophosphamide, IV immunoglobulin, rituximab)

Corticosteroid usage following completion of the prednisolone taper is permissible as part of routine clinical management. The use of corticosteroids in such circumstances should be documented appropriately as a concomitant medication, and the event precipitating its usage should be appropriately documented as an adverse event.

Should the use of corticosteroids (aside from inhaled corticosteroids for bronchospasm) be considered as part of care during the course of the prednisolone taper, this medical management should be discussed with the medical monitor.

### **9.3. Treatment Compliance**

AVXS-101 will be administered as a 1-time IV injection.

### **9.4. Randomization and Blinding**

This is an open-label study.

## **10. STUDY PRODUCT MATERIALS AND MANAGEMENT**

AVXS-101 is manufactured in accordance with current Good Manufacturing Practices (cGMP). Investigational product accountability logs will be maintained by the clinical pharmacy.

### **10.1. Study Product**

AVXS-101

### **10.2. Study Product Dose and Dose Justification**

Patients will receive a 1-time dose of AVXS-101 at  $1.1 \times 10^{14}$  vg/kg, equivalent to the dose received by Cohort 2 in the Phase 1 study via IV infusion administered in the ongoing Phase 1 clinical study (AVXS-101-CL-101).

Two doses are being studied in the ongoing Phase 1 clinical study (AVXS-101-CL-101); the higher dose (dose received by the Cohort 2 patients) was chosen for the present study as preliminary data demonstrated both a dose response and significant clinical benefit thus identifying it as the proposed therapeutic dose. In the Phase 1 study, AVXS-101 demonstrated a dose response, with efficacy greater as observed by motor milestone achievement and CHOP-INTEND scores at the higher dose (received by Cohort 2) than the lower dose (received by Cohort 1). Direct testing of the actual lot of Investigational Medicinal Product (IMP) used in the AVXS-101-CL-101 study by an improved and more fully qualified analytical method has assigned a value of  $1.1 \times 10^{14}$  vg/kg to the actual dose received by Cohort 2 in this Phase 1 study. The same method has been used to establish an equivalent dose for the Phase 3 IMP. This vg/kg value has been further verified in an improved and more fully qualified SMN $\Delta$ 7 Mouse Biopotency assay to support a similar extension of mouse life time in direct comparative assessment between the Phase 1 and Phase 3 IMP.

### **10.3. Study Product Packaging and Labeling**

AVXS-101 kits are labeled with a specific kit number and batch/lot number assigned at the cGMP facility. The content of the labeling is in accordance with the local regulatory specifications and requirements.

### **10.4. Study Product Storage**

AVXS-101 kits will be stored in an appropriate, locked room under the responsibility of the Investigator or other authorized persons (e.g., pharmacists) in accordance with local regulations, policies, and procedures. Control of storage conditions, especially control of temperature (e.g., refrigerated/freezer storage) and information on in-use stability and instructions for handling prepared AVXS-101 should be managed in accordance with the Pharmacy Manual.

The vessel used for delivery of the vector should be resealed in the procedure room and processed for destruction and/or return to AveXis in accord with the Pharmacy manual and applicable biohazardous waste guidelines for disposal.

## **10.5. Study Product Preparation**

Preparation of AVXS-101 will be done aseptically under sterile conditions by a pharmacist and will arrive at the clinical site ready for infusion.

AVXS-101 will be received diluted with normal saline, as outlined in the Pharmacy Manual.

The total vector genome dose will be calculated based on the patient's body weight.

The dose-delivery vessel will be delivered to the designated pediatric intensive care unit (PICU) patient room or other appropriate setting (e.g., interventional suite, operating room, dedicated procedure room) with immediate access to acute critical care management. The vessel will be delivered in accord with the Pharmacy Manual.

## **10.6. Study Product Administration**

AVXS-101 infusion will be administered under sterile conditions in a PICU or other appropriate setting (e.g., interventional suite, operating room, dedicated procedure room) with immediate access to acute critical care management. AVXS-101 will be delivered 1-time through a venous catheter inserted into a peripheral limb vein (arm or leg) at a dose equivalent to the dose received by the second dosing Cohort in the Phase 1 study. AVXS-101 should be slowly infused over approximately 30-60 minutes, dependent upon total volume in accord with the Pharmacy Manual, utilizing an infusion set and pump in accordance with the Pharmacy Manual.

Following administration of gene replacement therapy, patients should return to an appropriate designated setting to ensure close monitoring of vital signs and adverse events. Vital signs will be continuously monitored throughout the gene replacement therapy infusion as described in [Section 12.1.3](#). Patients should be maintained in the PICU or other appropriate setting for 48 hours after the start of gene replacement therapy.

## **10.7. Dose Adjustment Criteria**

The study investigates a 1-time IV infusion of AVXS-101; no dose adjustments are possible.

## **10.8. Study Product Accountability**

The pharmacist or designee will maintain accurate records of the quantities of AVXS-101 received, dispensed, destroyed, and/or returned to AveXis. The pharmacist or designee will document the date and time of delivery of the dose vessel to the dose procedure room as well as the time the used vessel was returned to AveXis or destroyed as per the Pharmacy Manual.

## **10.9. Study Product Handling and Disposal**

All materials used for injection, including sterile drapes, needles, and syringes in contact with the vector must be sealed in leak-proof containers. All waste must be sealed in bags bearing the biohazard symbol and disposed of in a biohazard waste container.

All transfers must be done in spill-proof containers. Individuals manipulating the vector will be required to wear personal protective equipment, such as gloves.

Any quality issue noticed with the receipt or use of AVXS-101 (e.g., deficiency in condition, appearance, pertaining to documentation, labeling, expiration date, etc.) should be promptly reported to the Sponsor in accord with procedures outlined in the Pharmacy Manual.

Under no circumstances will the Investigator supply AVXS-101 to a third party, allow AVXS-101 to be used other than as directed by this clinical trial protocol, or dispose of AVXS-101 in any other manner.

## 11. ASSESSMENT OF EFFICACY

Efficacy will be assessed by achievement of the key developmental milestone of functional independent sitting for at least 30 seconds at the 18 months of age study visit and survival at 14 months of age (as defined in [Section 14.1.1.1](#)). The ability to thrive and the ability to remain independent of ventilatory support (as defined [Section 14.1.1.2](#)) will also be assessed at 18 months of age. Additional developmental milestones will be assessed using the Bayley Scales of Infant and Toddler Development (version 3©). Efficacy assessments will be performed at the times specified in the Table of Assessments ([Appendix 5](#)) and should be the first assessments performed at any scheduled visit. All post-treatment visits will be relative to the date on which gene replacement therapy is administered except the 14 and 18 months of age visits, which will be relative to the patient's date of birth.

Unless otherwise noted, visit windows for the outpatient follow-up visits are as follows:

- Days 7, 14, 21, and 30:  $\pm 2$  days
- Monthly visits starting at Month 2:  $\pm 7$  days
- 14 months of age visit: 0 to 14 days **after** the patient reaches 14 months of age
- 18 months of age/End of Study visit: 0 to 14 days **after** the patient reaches 18 months of age

